9.4 Safety and Tolerability Assessments

9.4.1 Adverse events

Where changes in severity are recorded in the Case Report Form (CRF), each separate severity of the adverse event (AE) will be reported in the listings, only the most severe will be used in the summary tables. A pre-existing condition is defined as an AE that starts before the subject has provided written informed consent and is ongoing at consent. A non-treatment emergent AE is defined as an AE which starts after informed consent but prior to dosing. A treatment-emergent AE is defined as an AE which occurs postdose or which is present prior to dosing and becomes more severe postdose.

All AEs and PCs will be listed. Treatment-emergent AEs will be summarized by treatment, severity and relationship to the study drug. The frequency (the number of AEs, the number of subjects experiencing an AE and the percentage of subjects experiencing an AE) of treatment-emergent AEs will be summarized by treatment, Medical Dictionary for Regulatory Activities (MedDRA) version 21.1 system organ class and preferred term. The summary and frequency AE tables will be presented for all causalities and those considered related to the study drug. Any serious AEs will be listed.

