9.2. Adverse Events

Investigators are responsible for monitoring the safety of subjects who have entered this study and for alerting Lilly or its designee to any event that seems unusual, even if this event may be considered an unanticipated benefit to the subject.

The investigator is responsible for the appropriate medical care of subjects during the study.

Investigators must document their review of each laboratory safety report.

The investigator remains responsible for following, through an appropriate health care option, AEs that are serious or otherwise medically important, considered related to the IP or the study. The subject should be followed until the event resolves, stabilizes with appropriate diagnostic evaluation, or is reasonably explained. The frequency of follow-up evaluations of the AE is left to the discretion of the investigator.

After the informed consent form is signed, study site personnel will record, via eCRF, the occurrence and nature of each subject's preexisting conditions. Additionally, site personnel will record any change in the condition(s) and the occurrence and nature of any AEs.

The investigator will interpret and document whether or not an AE has a reasonable possibility of being related to study treatment, study device, or a study procedure, taking into account concomitant treatment or pathologies.

A “reasonable possibility” means that there is a cause and effect relationship between the IP, study device, and/or study procedure and the AE.

Planned surgeries should not be reported as AEs unless the underlying medical condition has worsened during the course of the study.

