10.3.1. Safety Analyses

10.3.1.1. Clinical Evaluation of Safety

All IP and protocol procedure AEs and PCs will be listed, and if the frequency of events allows, safety data will be summarized using descriptive methodology.

The incidence of symptoms for each treatment will be presented by severity and by association with IP as perceived by the investigator. Symptoms reported to occur prior to study entry will be distinguished from those reported as new or increased in severity during the study. Each symptom will be classified by the most suitable term from the medical regulatory dictionary.

The number of IP- and device-related SAEs and any related PCs will be reported.

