6. TREATMENTS

The following is a list of the study treatment abbreviations that will be used in the TFLs.

Study Treatment Name	Abbreviation	Treatment order in TFL
125 mg LY3074828 PFS (Arm)	Reference 1	1
125 mg LY3074828 PFS (Thigh)	Reference 2	2
125 mg LY3074828 PFS (Abdomen)	Reference 3	3
125 mg LY3074828 AI (Arm)	Test 1	4
125 mg LY3074828 AI (Thigh)	Test 2	5
125 mg LY3074828 AI (Abdomen)	Test 3	6

Abbreviations: AI = Autoinjector; PFS = pre-filled syringe.

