11. CHANGES FROM THE PROTOCOL SPECIFIED STATISTICAL ANALYSES

There were no changes from the protocol specified statistical analyses.

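### SAP 9.4.1 leaves out the protocol's count of device-related SAEs and related product complaints and plans no AE summary by device or procedure causality, yet SAP 11 declares no changes

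*SAP*

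**What the plan says.** SAP 9.4.1 gives listings first: "All AEs and PCs will be listed", and serious AEs are listed as well. For tables it says: "Treatment-emergent AEs will be summarized by treatment, severity and relationship to the study drug". Frequencies by treatment, system organ class and preferred term follow, and then: "The summary and frequency AE tables will be presented for all causalities and those considered related to the study drug".

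SAP 6 fixes what treatment means: "The following is a list of the study treatment abbreviations that will be used in the TFLs". The list holds six entries, one for each combination of device (PFS or AI) and site (arm, thigh or abdomen).

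Protocol 9.2 has the investigator judge and document whether "an AE has a reasonable possibility of being related to study treatment, study device, or a study procedure". Protocol 9.2.1.1 requires adverse device events to be marked as such in the eCRF. On reporting, Protocol 10.3.1.1 says: "The number of IP- and device-related SAEs and any related PCs will be reported".

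SAP 3 says that the SAP takes precedence over the protocol's statistical section and that substantial differences will be identified. SAP 11 then says: "There were no changes from the protocol specified statistical analyses".

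**The concern.** The study is meant to bridge from the PFS to the AI, and Protocol 3.3 undertakes to evaluate the risks that the devices bring. The site collects the causality judgments needed for this. The SAP then keeps a single causality cut, relation to the drug. That is the least informative cut here, because the drug product, dose, concentration and volume are the same in every arm (Protocol Table AMBE.2). The arms differ in device and site.

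At stake is whether the report shows, in a planned table, how many events were attributed to the device or to the injection procedure, and whether it gives the one device-related count that the protocol says will be reported.

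**Working it through.** The plan gives no figure on this point, so the check compares texts.

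**1. Protocol commitments against SAP outputs.**

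| Item | Protocol | SAP |
|---|---|---|
| TEAEs by severity and relation to the drug | 10.3.1.1: yes | 9.4.1: yes |
| AEs and PCs listed | 10.3.1.1: yes | 9.4.1: yes |
| Number of IP- and device-related SAEs | 10.3.1.1: yes | 9.4.1: SAEs listed, no count |
| Related PCs reported with that number | 10.3.1.1: yes | 9.4.1: PCs listed, no count |
| TEAEs by relation to device or procedure | Judged (9.2), device events marked (9.2.1.1), no table promised | No table |

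Rows three and four are a protocol commitment that the SAP does not carry over. Row five is information collected but not used; it is not a broken commitment.

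**2. Whether the protocol sentence still operates.** SAP 9.1 says that summary statistics appear only where the SAP details them, and SAP 9.4.11 sends safety assessments not detailed there to listings. On the SAP's own rules, a count it does not mention is not planned.

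**3. Where an event goes.** Assume that relation to drug, device and procedure is each recorded as yes or no. There are 2 × 2 × 2 = 8 patterns.

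- Drug yes: 4 patterns. These appear in the all-causality and the drug-related tables.
- Drug no, with device or procedure yes: 3 patterns. These appear in the all-causality tables only.
- All three no: 1 pattern. This also appears in the all-causality tables only.

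The second group cannot be separated from the third in any table that the SAP describes. Within the first group, events also attributed to the device cannot be separated from those attributed to the drug alone.

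**4. What can be recovered.** Each subject receives one injection in one arm, and each arm uses one device. All-cause subject counts therefore add exactly: AI = Test 1 + Test 2 + Test 3 and PFS = Reference 1 + Reference 2 + Reference 3, with 3 × 11 = 33 randomized per device. The same holds for drug-related counts. A device-related or procedure-related count cannot be obtained by adding columns. It needs a hand count from the listings.

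**The case against.** The case for the SAP is strong in several respects.

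- **Device-related TEAEs are counted.** A reader might infer that they are never counted. The all-causality tables include them, under columns that name the device. What is missing is the attribution.
- **Six-arm reporting follows the protocol.** Protocol 10.3.1.1 asks for incidence for each treatment, and Protocol 10.3.1.2.3 asks for injection-site events by device and site. Nothing promises AI and PFS totals for TEAEs, and site is randomized too.
- **The promised number is probably very small.** Protocol 3.2 reports no SAEs in any of the Phase 1 studies. Any SAE would be listed and could be counted by eye.
- **Attribution is subjective in an open-label study.** Staff know the device when they judge causality. Comparing all-cause events by randomized arm avoids that judgment, and those tables are planned. Pain is modelled for AI against PFS, and injection duration is summarized by treatment.
- **The table shells are a separate document.** SAP 3 places the detailed description of outputs there, and they were not available.

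These points show that the all-cause comparison of devices is available and that pooled columns are a matter of presentation. They do not explain why a count stated in the protocol is missing from a SAP that declares no changes. Nor do they supply a table for causality data that the protocol has the site collect.

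**Conclusion.** The point holds as a gap in descriptive safety reporting. One protocol commitment, the number of IP- and device-related SAEs and related PCs, is not carried into SAP 9.4.1, and SAP 11 does not say so. In addition, no cut by device or procedure causality is planned, so events attributed only to these drop out of the related-event tables. The primary PK and VAS analyses are unaffected.

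A reader might go further and infer that reporting by six arms loses information on the devices. With an assumed event rate of 5%, the chance of at least one event is 1 − 0.95^11 = 43% in an arm of 11 and 1 − 0.95^33 = 82% in a device group of 33. These figures do not measure a loss: the same 33 subjects are shown either way, and an event among them appears in one of three columns for that device. The documents also give no event rate. Nor does the protocol promise a count of complaints split by device.

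The conclusion rests on two assumptions: that the eCRF records the drug, device and procedure judgments so that they can be separated (Protocol 9.2.1.1 is explicit for the device, less so for the procedure), and that the table shells add nothing beyond the SAP text.

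**What to change.** In SAP 9.4.1, add:

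1. The number of IP- and device-related SAEs and of related PCs, as Protocol 10.3.1.1 states, with a definition of what makes a complaint related.
2. TEAE summary and frequency tables for events judged related to the study device, and the same for the study procedure.

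If the sponsor prefers not to add these, record the omission in SAP 11 with the reason. Check the table shells first; if the tables are already there, only the SAP text needs aligning.

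AI-total and PFS-total columns beside the six arms are optional. They save the reader an addition.

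The cost is some SAP and shell wording and a few tables from data already collected. Nothing changes for sites or subjects.

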9.4.2 Concomitant medication

Concomitant medication will be coded using the WHO drug dictionary (Version March 2018). Concomitant medication will be listed.

9.4.3 Clinical laboratory parameters

All clinical chemistry and hematology data will be summarized by parameter and treatment, and listed. Urinalysis data will be listed. Changes from baseline, Day -1, will also be presented. Additionally clinical chemistry, hematology and urinalysis data outside the reference ranges will be listed.

Values for any clinical chemistry, hematology and urinalysis values outside the reference ranges will be flagged on the individual subject data listings.

9.4.4 Vital signs

Vital signs data will be summarized by treatment together with changes from baseline, where baseline is defined as Day 1 predose. Figures of mean vital signs and mean changes from baseline will be presented by treatment.

Furthermore, values for individual subjects will be listed.

9.4.5 Electrocardiogram (ECG)

ECGs will be performed for safety monitoring purposes and will not be presented. Any clinically relevant findings will be reported as an AE.

9.4.6 Injection-Site Pain

Intensity of pain data will be quantified using a 100-mm validated VAS. The data will be listed and summarized by treatment and time point. In addition, the scores will be categorized into mild (0- to 30-mm), moderate (31- to 70-mm), and severe (71- to 100-mm), and presented in frequency tables by treatment and timepoint. Furthermore, scatter plots of the 1 minute, 5 minute, and 15-minute VAS scores will be presented by treatment and time point.

A linear fixed-effects model will be used to analyze the 1- and 5-minute post-injection pain VAS scores separately. The model will include device and injection site as fixed effects. The least squares means and differences between the AI (Test) and PFS (Reference) will be presented along with the corresponding 90% CI for the difference.

If the assumptions of this model appear to be violated, a non-parametric method may be used.

The distribution of the data will be explored prior to analysis to determine whether data transformation is required. It is possible that the pain scores will be 0, so if the distribution of the data implies that a log-transformation is required then the score may be updated to $\log(VAS+1)$ to allow for the inclusion of the 0 values in the analysis. If the assumptions of this model appear violated, a non-parametric method may be used.

The above analyses will also be repeated for each injection site separately.

SAS code similar to Section 9.3.2 will be used for this model.

9.4.7 Injection-Site Reactions

Injection-site reactions will be evaluated through the collection of pain assessments and specific site assessments for local tolerability, which will evaluate erythema, induration, pruritus, and edema. Data from injection-site evaluations (including pain), which are recorded as a result of specific questionnaires, will not be reported as AEs. However, injection site reactions may be reported as AEs if:

- a) Spontaneously reported by a subject.
- b) At the discretion of the principal investigator.

Injection-site reaction data will be listed and reactions reported as AEs will be summarized by treatment in frequency tables.

Any bruising or bleeding from the injection site will also be listed.

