3. INTRODUCTION

This SAP has been developed after review of the Clinical Study Protocol (final version dated 17 December 2018).

This SAP describes the planned analysis of the safety, tolerability and pharmacokinetic (PK) data from this study. A detailed description of the planned TFLs to be presented in the clinical study report (CSR) is provided in the accompanying TFL shell document.

The intent of this document is to provide guidance for the statistical and PK analyses of data. In general, the analyses are based on information from the protocol, unless they have been modified by agreement between Eli Lilly and Company and Covance Early Clinical (EC) Biometrics. A limited amount of information concerning this study (e.g., objectives, study design) is given to help the reader's interpretation. This SAP must be signed off prior to first subject administration for this study. When the SAP and TFL shells are agreed upon and finalized, they will serve as the template for this study's CSR.

This SAP supersedes the statistical considerations identified in the protocol; where considerations are substantially different, they will be so identified. If additional analyses are required to supplement the planned analyses described in this SAP, they may be performed and will be identified in the CSR. Any substantial deviations from this SAP will be agreed upon between Eli Lilly and Company and Covance EC Biometrics and identified in the CSR. Any minor deviations from the TFLs may not be documented in the CSR.

This SAP is written with consideration of the recommendations outlined in the International Conference on Harmonisation (ICH) E9 Guideline entitled Guidance for Industry: Statistical Principles for Clinical Trials¹ and the ICH E3 Guideline entitled Guidance for Industry: Structure and Content of Clinical Study Reports².

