9. STATISTICAL METHODOLOGY

9.1 General

Data listings will be provided for all data that is databased. Summary statistics and statistical analysis will only be presented for data where detailed in this SAP. For continuous data, summary statistics will include the arithmetic mean, arithmetic standard deviation (SD), median, min, max and N; for log-normal data (e.g. the PK parameters: AUCs and C_{max}) the geometric mean and geometric CV% will also be presented. For categorical data, frequency count and percentages will be presented. Data listings will be provided for all subjects up to the point of withdrawal, with any subjects excluded from the relevant population highlighted. Summary statistics and statistical analyses will generally only be performed for subjects included in the relevant analysis population. For the calculation of summary statistics and statistical analysis, unrounded data will be used.

Mean change from baseline is the mean of all individual subjects' change from baseline values. Each individual change from baseline will be calculated by subtracting the individual subject's baseline value from the value at the timepoint. The individual subject's change from baseline values will be used to calculate the mean change from baseline using a SAS procedure such as Proc Univariate.

Data analysis will be performed using SAS[®] Version 9.4 or greater.

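### SAP 9.4.7 lists the scheduled, form-recorded erythema, induration, pruritus and edema but tabulates only reactions reported as AEs, so the incidence of these signs by device and injection site has no planned table

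*SAP*

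**What the plan says.** SAP 9.4.7 opens by saying how local reactions will be judged: "Injection-site reactions will be evaluated through the collection of pain assessments and specific site assessments for local tolerability". The site assessments cover erythema, induration, pruritus and edema. Findings recorded through these questionnaires are not AEs by default. They may be reported as AEs by two routes: "Spontaneously reported by a subject" or "At the discretion of the principal investigator". Protocol 9.4.4.3 is more specific about the second route: the investigator records the reaction as an AE when it is judged clinically significant.

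The output sentence of SAP 9.4.7 is: "Injection-site reaction data will be listed and reactions reported as AEs will be summarized by treatment in frequency tables". Bruising and bleeding are to be listed. SAP 9.1 adds a general rule: "Summary statistics and statistical analysis will only be presented for data where detailed in this SAP".

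On the protocol side, the Schedule of Activities (Section 2) sets the assessments, and Section 9.4.4.3 puts them on a separate injection-site reaction form. Section 10.3.1.2.3, under the heading Injection-Site Assessments, says the incidence of these four signs will be both listed and summarized by device and injection site, whereas bleeding will only be listed. That section describes the four signs as AEs. SAP section 11 states: "There were no changes from the protocol specified statistical analyses".

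**The concern.** The study compares two delivery devices at three injection sites. Protocol 3.3 says device-based risks will be evaluated and names swelling and erythema among them. Protocol 5.1 lists injection-site assessments as one of the ways tolerability is judged. The scheduled form is the only source that asks about these signs in every subject at the same times, yet the SAP text gives it no count or percentage. The one planned frequency table holds reactions that passed a further step: the subject volunteered them or the investigator raised them. Subjects and staff know the device (Protocol 5.4), so that step could operate differently for the two devices.

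At stake is a descriptive result: whether the report shows the incidence of local signs by device and site as collected, or leaves the reader to count it from a listing.

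**Working it through.** No figure in the plan needs reproducing; the question is which outputs are planned. The texts can be set side by side.

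**Number of assessments.** In the Schedule of Activities the row for the four signs shows 0 and 0.25 hours on Day 1, then Days 2, 8 and 15. That is 2 + 3 = 5 per subject.

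**Planned SAP output for local data.**

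| Data | SAP section | Listing | Summary or frequency table |
|---|---|---|---|
| VAS pain score | 9.4.6 | yes | yes, by treatment and time point, plus a model at 1 and 5 minutes |
| Injection duration | 9.4.8 | yes | yes, by treatment |
| Reactions reported as AEs | 9.4.7 | yes | yes, by treatment |
| Erythema, induration, pruritus, edema from the form | 9.4.7 | yes | none |
| Bruising and bleeding | 9.4.7 | yes | none |

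**Could another section supply the table?** SAP 9.4.1 tabulates treatment-emergent AEs, which by default exclude form findings. The frequency tables in 9.4.6 are for pain categories. SAP 9.4.11 gives assessments not detailed elsewhere a listing only. With the rule in SAP 9.1, no summary arises by default. Count for the form-recorded signs: one listing, no table.

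**Does the AE table stand in for the form?** Not fully. A scheduled finding that is neither volunteered nor judged clinically significant is on the form and not in the AE table. An unsolicited reaction between visits can be an AE without being present at any scheduled assessment. The two sources overlap but answer different questions.

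**Protocol against SAP.** Protocol 10.3.1.2.3 can be read in two ways.

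- Literal: it covers AEs only. The SAP's AE table by treatment then delivers it, because the treatments in SAP section 6 ("The following is a list of the study treatment abbreviations that will be used in the TFLs") are the six device-by-site combinations. SAP section 11 is true.
- By context: the heading matches that of Protocol 9.4.4.3, the four signs are the ones on the form, and AE summaries are already covered in Protocol 10.3.1.1. The section then covers the scheduled findings, and the SAP is narrower without saying so.

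The wording does not decide between them.

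**The case against.** The strongest reply is that nothing has been dropped. Protocol 9.4.4.3 separates form findings from AEs, so the term has a meaning in Protocol 10.3.1.2.3, and the SAP delivers exactly an AE table by device and site. A reader might infer that the SAP silently abandons a protocol analysis and that its section 11 is wrong. The documents do not support that: on the literal reading section 11 is correct.

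A reader might also infer that the AE table is biased between devices and that the form would be free of bias. That goes too far as well. The form is completed by people who know the device, and pruritus depends on what the subject reports. Fixed assessment times remove the volunteering step but do not blind the rating. The AE route is also not arbitrary, since clinically significant reactions are meant to enter it, and injection-site reactions are AEs of special interest (Protocol 9.2.1.2). What goes untabulated is mainly solicited findings that were not judged clinically significant.

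Further points stand. The secondary endpoint is the incidence of TEAEs, and the four signs carry no hypothesis or decision rule. The data are listed, and arms of 11 can be counted by hand. SAP section 3 permits supplementary analyses, and the detailed table plan "is provided in the accompanying TFL shell document", which was not available for this review. Bleeding and bruising are also device risks named in Protocol 3.3, and the SAP only lists them.

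These points limit the weight of the concern but do not remove it. The output sentence in SAP 9.4.7, with SAP 9.1, is a stated rule rather than missing detail; followed as written, it gives no incidence for the scheduled signs. For bleeding the protocol itself plans only a listing, whereas for these four signs it speaks of incidence.

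**Conclusion.** The point holds as a minor improvement. The SAP text plans no tabulation of four local signs assessed five times in every subject, and its only incidence table for local signs is restricted to reactions reported as AEs. A conflict with Protocol 10.3.1.2.3 is possible but not established.

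The TEAE endpoint and the VAS pain analysis are unaffected. The documents give no basis for estimating how far form-recorded incidence would differ from AE incidence, so no numerical effect is claimed. The conclusion rests on the SAP text alone and assumes that the TFL shells do not already contain the table.

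**What to change.** Add one sentence to SAP 9.4.7, for example: *The number and percentage of subjects with each form-recorded sign (erythema, induration, pruritus, edema) and with any sign, at any scheduled post-dose assessment, will be summarized descriptively for each of the six treatments, separately from the AE table.*

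That is 4 signs + 1 row for any sign = 5 rows, by 6 treatments = 30 cells. A version by time point is optional. No test or model is needed.

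Clarifying in Protocol 10.3.1.2.3 whether the word AEs covers form findings is optional. An entry in SAP section 11 is needed only if the sponsor reads that protocol section as covering form findings and does not add the table. If the TFL shells already include it, only the SAP sentence needs aligning.

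The cost is one descriptive table from data already collected, with no added subjects, visits or samples.
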